## 6.1 Screening Period

For all treatment arms, the Screening window starts prior to first dose of study drug. Refer to a section 6.2 through Section 6.7 for detailed information on procedures performed and the schedule.

Waivers to the protocol will not be granted during the conduct of this trial, under any circumstances.

Safety laboratory analyses will be performed locally. Screening laboratory values must demonstrate subject eligibility, but may be repeated within the screening window, if necessary.

The ICF will be administered at the Screening visit to all subjects by qualified study staff. It must be signed and dated by the subject and the administering staff prior to the start of any other study procedures and its completion documented in source documents and in the eCRF. All screening tests and procedures must be completed within prior to the first dose of study drug according to the schedule shown in

The following will be performed at Screening (as specified in after informed consent has been obtained.

[figure not shown]
Inclusion and exclusion criteria will be assessed at Screening and recorded in the source documents and the eCRF.

- Disease (efficacy) assessments (refer to Section 6.4) with the bone marrow aspiration and biopsy, peripheral blood smear (PBS), and complete blood count (CBC) are collected during prior to the first dose of study drug. Pharmacodynamic bone marrow biomarker samples should be obtained at the same time (refer to Section 6.6).

#### 6.2 Treatment Period

All subjects who fulfill the inclusion/exclusion criteria who are continuing in the study will be registered in the IRT system prior to receiving study drug(s) on C1D1.

## 6.2.1 Prior and Concomitant Medications and Procedures

All prior and concomitant medications and procedures taken or conducted beginning when the subject signs the ICF, throughout the study, and after the last dose of study drug will be recorded in the source documents and eCRF.

Packed red cell and platelet transfusion history

## 6.2.2 Adverse Event Monitoring

Adverse events and serious adverse events (SAEs) will be recorded from the time a subject signs the ICF after the last dose of study drug. Refer to Section 10 for detailed information. Subjects experiencing AEs will be monitored with relevant clinical assessments and laboratory tests, as determined by the Investigator. Every attempt will be made to document resolution dates for ongoing AEs. The AE will be recorded on the AE page of the eCRF and in the subject's source documents. Photographs of skin rashes should be obtained whenever possible, anonymized, and stored appropriately for future retrieval.

## 6.2.3 Vital Signs and Oxygen Saturation

Vital signs include body temperature, blood pressure, pulse rate, and respiration rate will be recorded at screening and during the study at various time points for safety monitoring as described in the Table of Events

Serial vital signs will be obtained during each CC-95251

and at 30 (s 10 minutes)

after the EOI and recorded with vital signs time points.

Additional vital signs should be obtained as clinically indicated per the Investigator's assessment. All measurements will be captured in the source documents and eCRF.

# 6.2.4 Physical Examination and ECOG Performance Status

Physical examination, including height and weight, and Eastern Cooperative Oncology Group (ECOG) performance status will be performed at the visits listed in and Results for both will be recorded in the source documents and results for height, weight and the ECOG PS will also be collected on the eCRF.

Physical examination findings will be classified as either normal or abnormal. If abnormal, a description of the abnormality and clinical significance will be provided in the source documents. Clinically significant changes from baseline will be recorded in the AE section of the eCRF.

## 6.2.5 Pregnancy Test

All subjects will be informed about pregnancy-related risks prior to the first dose of study drug to ensure compliance with all requirements for pregnancy prevention.

A SCBP is defined as a sexually mature individual who has:

- Not undergone a hysterectomy (the surgical removal of the uterus) or bilateral oophorectomy (the surgical removal of both ovaries), or
- Not been naturally postmenopausal (amenorrhea following cancer therapy does not rule out childbearing potential) for at least 24 consecutive months (eg, has had menses at any time in the preceding 24 consecutive months).

The Investigator will classify a subject as a SCBP according to this definition. Pregnancy testing is not required for non-SCBP subjects, but justification must be recorded in the eCRF and the source document. Pregnancy testing will be conducted by the local laboratory.

For a SCBP, pregnancy testing will be conducted at the visits listed in

A serum pregnancy ( $\beta$ -hCG) test with sensitivity of at least 25 mIU/mL is to be obtained at Screening and serum or urine pregnancy test (based on Investigator's discretion) within 72 hours prior to C1D1 of study treatment. The subject may not receive study drug until the Investigator has verified the two screening pregnancy tests to be negative.

- A quantitative serum or urine pregnancy test (based on Investigator's discretion and minimum test sensitivity [25 mIU/mL]) should be done within 72 hours prior to Day 1 of every cycle, and at the EOT visit. The subject may not receive study drug until the Investigator has verified the pregnancy test to be negative.
- A SCBP or a subject who is able to impregnate their partner must avoid blood/egg/semen/sperm donation and activities that could lead to conception for at least after the last dose of CC-95251 and 6 months (or longer if required by local regulations) for SCBP or 3 months (or longer if required by local regulations) for subject who is able to impregnate their partner, after the last dose of azacitidine.

Results for pregnancy tests will be recorded in the source document and eCRF.

## 6.2.6 Clinical Laboratory Tests

The following laboratory assessments will be performed at the Screening visit and/or during the study at the time points as described in days should . Laboratory assessments will be recorded in the source document and eCRF and are the following:

•	Hematology:	
•	Serum chemistry:	

- For an individual subject, the type of sample drawn (either serum or plasma) for chemistry assessment should be consistent across all collection time points.
- Special chemistry:

- Coagulation:
- Urinalysis or dipstick
  - microscopy in the event of a positive (1+ or greater) blood or protein
  - 24-hour collection for creatinine clearance and protein quantification in the event of 2+ or greater protein
- Creatinine clearance determination using the Cockcroft-Gault equation required at Screening to fulfill inclusion criteria (refer to Section 4.2).

## 6.2.7 12-Lead Electrocardiograms

When subjects are being

treated with CC-95251 in combination with azacitidine, the ECG will be done prior to CC-95251 administration.

Investigators will make clinical decisions based on their interpretation of the ECG results and provide their overall assessment of the ECG in the eCRF. Clinically significant changes from baseline will be recorded in the AE section of the eCRF.

#### 6.2.8 Left Ventricular Ejection Fraction

will be conducted at Screening in all subjects, and as clinically indicated. If clinically indicated, follow-up assessments should use the same procedure used at the screening assessment.

Clinically significant changes for these assessments will be documented on the AE section of the eCRF.

#### 6.2.9 End of Treatment

An EOT evaluation (refer for procedures) should be performed for subjects who are discontinued from treatment for any reason as soon as possible after the decision to permanently discontinue treatment has been made

#### 6.3 Follow-up Period

### 6.3.1 Safety Follow-up

All subjects will be followed for after the last dose of study drug for AE reporting. In addition, concomitant medication use, SAEs made known to the Investigator at any time thereafter that are suspected of being related to study drug are to be reported until such SAEs have recovered (returned to baseline), recovered with sequelae, or death (due to the SAE) as described in Section 10.1. Subjects will also be followed for all AEs (SAEs and non-serious AEs) associated with confirmed or suspected SARS-CoV-2 infection until resolution, the condition stabilizes, the event is otherwise explained, the event is deemed irreversible, the subject is lost to follow-up, or for suspected cases, until SARS-CoV-2 infection is ruled-out.

The safety follow-up contact may be done by telephone if the subject is unable or unwilling to come in for the PK and ADA sampling.

## 6.3.2 Efficacy Long Term Follow up

After EOT visit, subjects without documented progression of disease (or relapse) or start of a new anticancer therapy will have efficacy evaluations

or until progression of disease (or relapse), initiation of a new anticancer therapy, withdrawal from the study, death, or the End of Trial, whichever comes first. A bone marrow evaluation will be completed

and as clinically indicated during the Follow-up Period.

Information (including dates) on new anticancer therapies initiated will be collected until withdrawal from the study, death, or the End of Trial, whichever comes first.

## 6.3.3 Survival Follow up

After EOT visit, all subjects will be followed according to the schedule for the efficacy long term
follow-up (refer to Section 6.3.2) for survival or until death, lost to follow-up, or
the End of Trial, whichever occurs first. Survival follow-up
The Follow-up Period will document survival and new anticancer therapies
The state of the s
6.4 Efficacy Assessment
Blood and Bone Marrow Aspirate and/or Biopsy
Bone marrow (BM) aspiration and/or biopsy for disease burden assessments will be collected to
be evaluated for at Screening, end
In addition, bone marrow
aspirates (BMA) or biopsies (BMB) are performed to confirm complete remission (CR) or
morphologic CR with incomplete hematologic recovery (CRi) or morphologic CR with partial
hematologic recovery (CRh), relapse after CR, CRi, or CRh (as assessed by the Investigator based
on CBC with WBC differential results), or disease progression. Additional aspirates and/or
biopsies will be collected as clinically indicated, based on Investigator's medical judgement. Both
bone marrow aspirate and biopsy samples are mandatory at Screening
thereafter, a bone marrow aspirate alone is sufficient, but a biopsy must be collected if the aspirate
is not available and may be collected in addition to the aspirate per institutional practice.

Response to treatment will be assessed by Investigator using local laboratory results according to modified 2017 European Leukemia Network (ELN) AML Response Criteria (Döhner, 2017) for AML and modified IWG Response Criteria (Cheson, 2006) for MDS based on reported hematology laboratory parameters, peripheral blood smear, bone marrow aspirates and/or biopsies. Hematologic response/transfusion dependence will also be evaluated. In addition, CR with partial hematologic recovery (CRh) will be reported for both AML and MDS (Bloomfield, 2018).

AML response criteria will be summarized by best overall response categories: complete remission rate (CRR) defined as CR + CRi + CRh, and objective response rate (ORR, all responses of CR [ie, CRMRD-, morphologic CR, CRh, CRi] + morphologic leukemia free state [MLFS] + partial remission [PR]). For MDS, the CRR is defined as CR, ORR includes all responses (CR + CRh + marrow CR + PR). The efficacy variable of focus will be CRR and ORR. Other measures of clinical activity include duration of remission, duration of response, stable disease rate (MDS only), relapse-free survival, event-free survival, progression-free survival, time to remission/response, transfusion independence, time to AML transformation for MDS subjects, and overall survival (OS) rates at 6 and 12 months.

The site will ensure peripheral blood, plasma and BMA/BMB samples are collected and sent to the central lab for exploratory testing at the time of each bone marrow collection as detailed in the Biomarkers Section 6.6.

#### Progressive disease for AML will be defined as:

- A > 50% increase in bone marrow blast count percentage from the baseline (screening) bone marrow blast count (a minimum 15% point increase is required in cases with <30% blasts at baseline; or persistent bone marrow blast count > 70%, over at least 3 months; without at least a 100% improvement in ANC to an absolute level (> 0.5 x 10^9/L) and/or platelet count > 50 x 10^9/L non-transfused), or
- A > 50% increase in peripheral blasts (WBC × % blasts) to > 25 x  $10^9/L$  (> 25,000/ $\mu$ L) (in the absence of differentiation syndrome), or
- New extramedullary disease.

The date of progressive disease is defined as the first date that there was either a > 50% increase in BM blast count from baseline, a persistence of BM blasts > 70% in subjects with a baseline BM blast count of > 70%, or a doubling of the peripheral blood (PB) blast count.

Treatment failure will be defined as progressive disease or not achieving at least partial remission (PR) by the end of the treatment period. Subjects may continue treatment if they are deriving benefit from treatment without unacceptable toxicity (any CR, MLFS, PR, or SD with demonstrated clinical benefit eg, reduction in transfusion burden), as judged by the Investigator, or until disease progression, loss of clinical benefit, unacceptable toxicity, or decision to withdraw by subject or Investigator. Failure to achieve a response while simultaneously not meeting the criteria for progressive disease will be considered stable disease.

Subjects who discontinue study treatment for reasons other than disease progression (or relapse) or start of a new anticancer therapy will have disease assessments according to the specified

assessment schedule (refer to Section 6.3.2) until progression (or relapse) and/or initiation of new anticancer therapies. For subjects who have discontinued study treatment due to relapse or progression or start of a new anticancer therapy, follow up can be performed by site visits or phone calls. Subjects will be followed they have died, are lost to follow up, withdraw consent for further data collection, or until study closure.

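### The rule that dates AML progression does not match the criteria that define it: extramedullary-only progression gets no date, and some blood progressions get none or a late one

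*Combined protocol and SAP*

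**What the plan says.** Section 6.4, under the heading on progressive disease for AML, gives three criteria joined by 'or':

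- **Marrow.** One form is a rise of more than 50% over the screening blast percentage, with a qualifier for low baselines: "a minimum 15% point increase is required in cases with <30% blasts at baseline". The second form covers blasts that stay high, worded as "or persistent bone marrow blast count > 70%, over at least 3 months". A condition on neutrophil and platelet improvement also applies.
- **Blood.** "A > 50% increase in peripheral blasts (WBC × % blasts"), with the count reaching more than 25 × 10⁹/L.
- **Extramedullary.** "New extramedullary disease", sufficient alone.

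The next paragraph sets the date: "The date of progressive disease is defined as the first date that there was either" a marrow rise above 50% from baseline, marrow blasts staying above 70% in a subject whose baseline was above 70%, "or a doubling of the peripheral blood (PB) blast count". The sentence is complete and shows no redaction gap.

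Table 3 lists PFS and event-free survival as secondary endpoints in dose expansion. Section 9.6 plans Kaplan-Meier analysis, with PFS rates at 6 and 12 months.

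**The concern.** A Kaplan-Meier analysis needs one date for each event. Here a subject can meet PD by one set of tests and be dated by another. Two routes lack a matching date test: new extramedullary disease alone, and a blood blast rise that meets the criterion but falls short of doubling. An analyst following the text would have to improvise a date, censor the subject or wait for some later event. Those choices give different PFS curves from the same data.

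A later doubling may not be on record. After the end-of-treatment visit, Section 6.3.2 continues efficacy evaluations "or until progression of disease (or relapse), initiation of a new anticancer therapy", among other end points. For subjects who stopped because of progression, Section 6.4 says "follow up can be performed by site visits or phone calls".

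Two further points need reconciling. The date tests omit the 15-point marrow minimum and the 25 × 10⁹/L blood floor, so a date can fall before PD is met. The date sentence also attaches a baseline condition to the persistent-blast route that the criterion does not state.

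**Working it through.** The plan gives no figure to reproduce. The check sets each criterion against the date test that should serve it.

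**Extramedullary route.** None of the three date tests concerns extramedullary disease. If it is the only evidence of progression, the rule returns no date. No assumption is needed.

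**Blood route.** Neither the criterion nor the doubling test names its reference value; baseline p (× 10⁹/L) is assumed for both.

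- PD is met above max(1.5p, 25).
- The date test is met at 2p.
- They coincide where 2p = 25, that is p = 12.5. Above that, PD comes first; below it, the date test comes first.

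| Baseline p | PD met above | Date test at | Difference |
|---|---|---|---|
| 5 | 25 | 10 | date 15 early |
| 10 | 25 | 20 | date 5 early |
| 12.5 | 25 | 25 | none |
| 13 | 25 | 26 | date 1 late |
| 15 | 25 | 30 | date 5 late |
| 20 | 30 | 40 | date 10 late |
| 30 | 45 | 60 | date 15 late |
| 40 | 60 | 80 | date 20 late |

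A subject rising from 20 to 32 has PD (+60% and above 25). There is no date unless blasts later reach 40 or a marrow date test is met.

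To express the gap as time, assume exponential blast growth, which the documents do not state:

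- Late: log2(30/25) = 0.26 doubling times at p = 15. From p = 25/1.5 = 16.7 upward it is log2(2/1.5) = 0.42.
- Early: log2(25/10) = 1.32 doubling times at p = 5, and log2(25/20) = 0.32 at p = 10.

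**Marrow rise, baseline b below 30%.** The date test is met above 1.5b. PD also needs b + 15. The gap is (b + 15) − 1.5b = 15 − 0.5b points:

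| Baseline b | Date test above | PD needs | Gap (points) |
|---|---|---|---|
| 10% | 15% | 25% | 10 |
| 20% | 30% | 35% | 5 |
| 25% | 37.5% | 40% | 2.5 |

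The gap closes at b = 30%. From there upward the two percentage thresholds agree.

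**Persistent marrow blasts above 70%.** The date sentence requires a baseline above 70%; the criterion does not say so. The criterion can be read as implying it, so this is a wording conflict and not a proven undated route.

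**Other places a date might be given.** Table 19 in Appendix C refers to PD criteria without defining or dating them. Section 9.6 defines no event date. No other readable text supplies one.

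**The case against.** The strongest reply concerns weight. The primary endpoint is safety, the key efficacy variables are CRR and ORR, and all analyses are descriptive. Table 3 places efficacy in dose expansion, so only the two AML cohorts of Part B and Part D are touched. No readable decision rule uses PFS, and a late blood date trails by at most 0.42 doubling times if growth is exponential. All of this stands. It limits the consequence but does not reconcile the text.

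Section 6.4 also calls for marrow sampling to confirm progression, and Section 6.2.9 requires an end-of-treatment evaluation. A confirmatory marrow with a rise above 50% would supply a date. That is partial relief only, since the marrow need not show such a rise. It does mean that loss of a later doubling is possible rather than demonstrated.

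The Table 3 footnote on efficacy is unreadable, as is much of Sections 4.3, 9.2 and 9.3. A dating convention could sit in lost text, and it is unknown how many subjects enter with blood blasts above 12.5 × 10⁹/L. The finding is accordingly limited to the readable text. A convention elsewhere would still conflict with the explicit sentence in Section 6.4.

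Finally, the date sentence may intend the onset of the rise that later becomes PD. That could explain the early dates. It cannot explain a blood date test stricter than the criterion, or the absent extramedullary test.

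**Conclusion.** The concern holds. As written, the rule gives no date for extramedullary-only PD, and no date or a late one for blood PD short of doubling. The first follows directly from the text. The second applies above 12.5 × 10⁹/L and rests on baseline being the reference. The early dates matter only if onset dating is not intended, and the doubling-time figures rest on assumed exponential growth. The documents give no frequencies.

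The reach is PFS, its 6- and 12-month rates, and event-free survival if PD is an event in it. Safety, CRR and ORR are unaffected. An analyst could reasonably use the investigator's assessment date, but the readable protocol states a different rule. This should be corrected before PFS is analysed.

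**What to change.** Replace the date sentence in Section 6.4 with: *The date of progressive disease is the date of the first assessment at which any one of the criteria above is met, including new extramedullary disease.*

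Add two clarifying lines:

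- the reference value for the peripheral blast rise;
- which assessment dates the persistent-blast route, and whether that route requires a baseline above 70%.

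If the sponsor intends onset dating, the text should say so and give every PD route its own date test.

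The cost is one replaced sentence and two added lines. No PD threshold changes, and no extra data, visits or subjects are needed. Under Section 12.5 a protocol amendment needs IRB/EC approval unless it is administrative. An event-date rule in the analysis plan could serve the same purpose, provided that it explicitly supersedes the Section 6.4 sentence.

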#### Molecular and cytogenetic studies in BM may be omitted:

- At the Screening, if they were completed within the to enter on the eCRFs.
- •

The bone marrow aspiration and core sampling (biopsy) should be performed according to the standard of care and analyzed at the local site's laboratory in accordance with the International Council for Standardization in Hematology Guidelines (Lee, 2008).

[figure not shown]
#### Minimal residual disease

The minimal residual disease (MRD) response rate and MRD conversion rate will also be assessed as efficacy variables. MRD negative CR (CRMRD-), combined rate of CRs (cCRR = CR + CRMRD- + CRi + CRh in AML and CR + CRMRD- in MDS) will be assessed (Bloomfield, 2018).

MRD assessments will be performed in BMA or BMB at disease assessment timepoints using a flow cytometry-based and/or NGS-based method performed by central laboratory (refer to Biomarkers Section 6.6).

Testing for MRD will be performed locally, as applicable, per institutional guidelines in AML subjects with complete response in order to permit efficacy assessment according to ELN response criteria (Dohner, 2017).

#### Packed red blood cell and platelet transfusions

Packed red cell and platelet transfusion history before beginning the study treatment, continuous, and until End of Treatment or efficacy follow-up, whichever occurs later will be collected.

#### 6.5 Pharmacokinetics

Samples will be collected for PK and immunogenicity assessment for subjects at the time points indicated in for each study part.

All on-treatment PK time points are intended to align with days on which study treatment is administered. All predose samples should be taken prior to the start of CC-95251 infusion. If it is known that a dose is going to be delayed, then collect the predose sample just prior to the delayed dose. However, if a predose sample is collected but the dose is subsequently delayed, do not collect an additional predose sample.

[figure not shown]

[figure not shown]
Dosing and sample collection information, including CC-95251 dose level, dosing date, dosing time, infusion time, and actual PK blood sampling time, should be accurately documented on the appropriate source documents and eCRF (refer to Table 5). If the infusion was interrupted, the interruption details will also be documented on the eCRF.

[figure not shown]
Pharmacokinetics of CC-95251 will be derived from serum concentration versus time. The pharmacokinetic parameters including but not limited to the ones shown in Table 5 will be assessed where feasible.

Table 5: Pharmacokinetic Parameters

C max	Maximum observed serum concentration			
$C_{min}$	Minimum observed serum concentration			
T max	Time of maximum observed serum concentration			
AUC (0-T)	Area under the concentration-time curve from time zero to time of last quantifiable concentration			
C trough	Trough observed serum concentration			
AUC(TAU)	Area under the concentration-time curve in a dosing interval			
CLT	Total body clearance			

Concentration analyses for CC-95251 will be performed by validated bioanalytical method(s).

[figure not shown]
Additionally, residu	al bioanalytical	samples	will 1	be	archived	and	may	be	used	for	potential
exploratory bioanaly	sis (including b	ut not lim	nited to	) :							

Detailed instructions for the PK and immunogenicity blood collection, labeling, processing, storage, and shipping will be provided to the site in the laboratory manual.

